5.1. Basic Definitions

Study Drug

Study drug for this study refers to VM202 or placebo.

5.2. Study Points of Reference

Study Day 0

The date of the first study drug administration or the date of enrollment for subjects who were not administered any dose of study drug.

Study Day

For protocol defined assessments, the number of days from the day 0 visit to a date of interest, is calculated as:

Visit day = date of interest - date of study day 0.

Note that per CDISC dataset standards, the standard study day in the datasets will actually be calculated as:

If the date of interest is >= first dose date:

Study day= date of interest- date of first dose + 1 (there is no day 0)

If the date of interest is < first dose date:

Study day= date of interest- date of first dose + 1

5.3. Study Specific Definitions

5.3.1. Definitions of Safety Outcomes

Adverse Event (AE)

An adverse event (AE) is the development of an untoward medical occurrence or the deterioration of a pre-existing medical condition following or during exposure to an investigational product, whether or not it is considered causally related to the product.

Based on the protocol, conditions or diseases that are chronic but stable are NOT considered as AEs, nor are changes in a chronic condition or disease that are consistent with natural disease progression.

Serious AE (SAE)

Any untoward medical occurrence which results in death; is a life-threatening experience; requires hospitalization (admission to hospital with a stay > 24 hours) or prolongation of an existing hospitalization which is not specifically required by the protocol or is elective; results in permanent impairment of a body function or permanent damage to a body structure; or requires medical or surgical intervention to preclude permanent impairment of a body function or permanent damage to a body structure.

5.3.2. Definitions of Efficacy Endpoints

Complete Wound Closure

Defined as skin 100% re-epithelization without drainage or dressing at any time during the study. Complete wound closure will be assessed by the investigator at the sites and 100% reconciled with the ARANZ data, when possible. The primary analysis will be based on the eCRF page "Photography and Measurement of Ulcer in Target Leg".

Wound Volume, Wound Perimeter, Wound Area, and Wound Depth

The target wound's volume, perimeter, area, and depth will be measured using ARANZ Silhouette products at baseline and every scheduled post-baseline visit until wound closure.

Formation of New Foot Ulcer

Defined as a newly formed non-healing or poorly healing full-thickness wound, below the ankle on the target foot; these will be identified solely based the AE data provided by the site. The AE verbatim term will be scanned for the text "ULCER" and for "LEFT" vs. "RIGHT". The side will be matched with the target limb side from the eCRF and, if no information on site is present, it will be assumed that the new ulcer is on the target limb.

Major amputation

Defined as an amputation of the lower extremity above the ankle; these will be identified based on a blinded review of the AE data. The affected leg identified in the verbatim term on the AE electronic case report form (eCRF) and target foot noted on Physical Exam eCRF will be used to determine if the major amputation was in the target limb. These amputations will be noted in the clinical study report (CSR).

Minor amputation

Defined as an amputation of a foot or any parts of a foot such as toes; these will be identified based on a blinded review of the AE data. The affected leg identified in the verbatim term on the AE eCRF and target foot noted on Physical Exam eCRF will be used to determine if the minor amputation was in the target limb. These amputations will be noted in the CSR.

Cardiff Wound Impact Questionnaire (CWIQ)

The CWIQ is a patient-reported outcome measure designed to assess the impact of leg and diabetic foot ulcers on patient health-related quality of life (HRQoL). There are 3 domains/subscales:

- well-being (7 items, graded on a 5-point scale [1 = strongly disagree to 5 = strongly agree])
- physical symptoms and daily living (24 items, graded on a 5-point scale [1 = not at all to 5 = always])

• social life (14 items, graded on a 5-point scale [1 = not at all/not applicable to 5 = very])

The first and third subscales measure both the experience of the given concerns/symptoms and the stress they caused the patient; this duplication was not present in the referenced development and validation report cited below. In addition, there are Overall Quality of Life questions (2 items graded on a 11-point scale [0 = my quality of life is the worst possible or not at all satisfied to 10 = my quality of life is the best possible or very satisfied]).

Individual items are scored based on the CWIQ scoring instructions and summed for each domain and the Overall Quality of Life items. The tool is scored in such a way that a high score represents a 'good' HRQoL and a low score represent a 'poor' HRQoL. With the exception of one item in the well-being domain ("I am confident that the wound(s) I have will heal"), all items are scored 5-1 within the subscales reading from left to right on the questionnaire.

Reference:

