The number of copies of VM202 in whole blood will be determined at Day 0 (pre-injection, and 2 hours $[\pm 1 \text{ hour}]$ post injection), at Day 14 (pre-injection, and 2 hours $[\pm 1 \text{ hour}]$ post injection), at Day 28 (pre-injection, and 2 hours $[\pm 1 \text{ hour}]$ post injection), at Day 42 (pre-injection, and 2 hours $[\pm 1 \text{ hour}]$ post injection) at Day 60 and at Day 90.

Measurement of target ulcer will be performed at each follow-up visit until complete wound closure is achieved or until study exit. ABI, TBI, and the Cardiff Wound Impact Questionnaire (CWIQ) will be conducted on Day 0, Day 120, and Day 210 Visits. TcPO₂ will be assessed as a substudy at 3 -10 sites on Day 0, Day 120, and Day 210 Visits. Adverse events will be recorded after first study drug administration and throughout the 7-month follow-up period.

SCHEDULE OF EXAMINATIONS

Screening (Day -45 to Day -7)

Day 0

Day 14 ± 3 days

Day 28 ± 3 days

Day 42 ± 3 days Day 60 ± 3 days Day 74 ± 3 days Day 90 ± 7 days Day 120 ± 7 days Day 210 ± 14 days

STUDY ENDPOINTS

The primary study endpoint is the proportion of subjects with a target wound closure by the 4-month follow-up. Complete wound closure is defined as skin re-epithelization without drainage or dressing (primary endpoint), confirmed at a second scheduled or unscheduled visit two weeks $(14 \pm 5 \text{ days})$ later (secondary endpoint). Active and placebo arms will be compared to determine treatment effect.

Other endpoints will include:

- Time to complete healing of foot ulceration in each group
- Percent change in wound size
- Formation of new ulcers on the target foot
- Change in CWIQ
- Major amputations
- Minor amputations
- Change in ABI
- Change in TBI
- Change in TcPO₂ at select sites only

TABLE OF CONTENTS

INVE	STIGATOF	r's Agre	EEMENT	3
STUD	Y SYNOP	SIS		4
TABL	LE OF CON	NTENTS		10
ABBI	REVIATIO	NS		14
PERS	ONNEL A	ND FACII	LITIES	16
1.	BACKGR	OUND		20
	1.1.		aling Foot Ulcers	
			PAD and Diabetes – Two Roads to a Chronic Wound	
	1.2.		Healing	
	1.3.	Current	Treatment Options	22
	1.4.	Unmet	Medical Need	22
	1.5.		cyte Growth Factor (HGF) and Wound Healing	
	1.6.	VM202	2 for the Treatment of Chronic Foot Ulcers	
		1.6.1.	J	
		1.6.2.	VM202 Wound Healing Data - Rationale	
		1.6.3.	Phase I Study of VM202 in Patients with Critical Limb Ischemia	
		1.6.4.	Phase II Study of VM202 in Patients with Critical Limb Ischemia	
		1.6.5.	Clinical Experience Conclusions	
	1.7.	Study a	and Dose Rationale	28

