3. STUDY DESIGN

This is a phase III, randomized, double-blind, placebo-controlled, multicenter, 7-month study designed to assess the safety and efficacy of intramuscular injections of VM202 in the calf of diabetic patients with chronic nonhealing foot ulcers and concomitant PAD. Subjects with confirmed PAD and diabetes aged \geq 18 years to \leq 80 years diagnosed with nonhealing foot ulcers will be screened for study eligibility after giving informed consent.

At Screening, standard of care will be initiated that will continue for the duration of the study, as follows:

- Surgical debridement of necrotic tissue or devitalized tissue
- Use of appropriate off-loading when ambulating
- Maintenance of moist wound environment

Three hundred patients (from up to 30 study centers) who meet the eligibility criteria will be randomized in a 2:1 ratio to one of two treatment groups: 200 patients with VM202 (16 mg) plus standard of care or 100 subjects with placebo plus standard of care, respectively. Safety will be monitored throughout the study by an independent Data Safety Monitoring Board (DSMB, Section 8.5).

Patients will receive intramuscular injections in the ipsilateral calf of the affected foot with the target ulcer of either VM202 or placebo on Day 0, Day 14, Day 28, and Day 42 as follows:

Treatment: Days 0, 14, 28, and 42

TREATMENT]	DOSE VM20	FINAL DOSE		
GROUP	DAY 0	DAY 14	DAY 28	DAY 42	VM202 (mg)
VM202	4	4	4	4	16
Placebo	0	0	0	0	0

0 indicates injections of Placebo

VM202 will be delivered in a solution of 0.5 mg VM202 / mL. All subjects will receive sixteen (16) 0.5-mL intramuscular injections of VM202 or placebo at each injection visit.

The schedule of study visits and the clinical parameters that will be measured at the visits are summarized in Table 1 to Table 3 below.

The subjects' target ulcer will be evaluated by photograph, surface area, depth, perimeter and volume measurements. Subjects must have a non-healing ulcer on Day 0 that meets study entry inclusion criterion # 5 and does not meet exclusion criterion #6 to be eligible for study participation. Subjects will continue to come to the clinic once a week for dressing changes and wound assessment until the ulcer has healed or study exit, whichever comes first. Measurement of the target ulcer will be performed at each follow-up visit until complete wound closure or study exit.

Further details on the study procedures and conduct are provided in the protocol.

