5.4. Derived Variables

Baseline Value

The last non-missing value prior to first dose of study drug. If a subject does not receive any study drug, baseline is the latest recorded measurement on or before the randomization date.

Change from Baseline Value

Change from baseline value is the arithmetic difference between a value of interest and a baseline value: Change from baseline value = (value of interest – baseline value).

Percent Change from Baseline Value

The ratio of the arithmetic difference between a value of interest and the baseline value to the baseline value multiplied by 100: (Change from Baseline / Baseline) \times 100.

Time to Complete Wound Closure

Time to complete wound closure is the time interval (in days) from Day 0 to the date of the first visit date within the allowed visit window where wound closure is so indicated by the investigator. If a subject has not experienced complete wound closure, the subject will be considered censored at the subject's end of study date.

Time to a major amputation in the target limb

Time to a major amputation in the target limb is the time interval (in days) from Day 0 to the earliest date of a reported AE of an amputation of the lower extremity above the ankle of the target limb.

Time to a minor amputation in the target limb

Time to a minor amputation in the target limb is the time interval (in days) from Day 0 to the earliest date of a reported AE of an amputation of a foot or any parts of a foot such as toes on the target limb.

Absolute Differentials

If not provided by the individual study center labs, values for the absolute differentials (i.e., neutrophils, lymphocytes, monocytes, eosinophils, and basophils) will be calculated by multiplying the WBC count by the corresponding percent differential in the total WBC count. Results should be rounded to the nearest hundred for units equivalent to $10^3/\mu L$.

Percent Differentials

If not provided by the individual study center labs, values for the percent differential (i.e., neutrophils, lymphocytes, monocytes, eosinophils, and basophils) will be calculated by dividing the corresponding absolute differential count by the total WBC count. Results should be rounded to the tenth of a percentage point.

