8. DATA HANDLING

8.1. General Principles of Data Handling

Data screening will be conducted in a blinded fashion periodically during the conduct of the study. The objective of the data screening is to assess the quantity, quality, and statistical characteristics of the data relative to the requirements of the planned analyses. Any questionable values or situations will be reported to the CDRC for blinded review and confirmation.

Except as noted below, the data source for all safety and efficacy endpoints will be the study's Electronic Data Capture database (DATATRAK). Extracts from the Interactive Web Response System used for randomization will be the data source for the randomized treatment. The actual treatment received will be determined from the randomized treatment with adjustments based

on externally noted protocol/procedural deviations. All wound measurement data will come from the ARANZ Medical study-specific database, and pharmacokinetic data (HGF serum levels and copies of VM202 in whole blood) will be provided by Inc.

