8.6. Handling of Missing and Incomplete Data

Subjects may have missing specific data points for a variety of reasons. In general, data may be missing due to a subject's early withdrawal from study, a missed visit, or a clinical parameter not measured at a particular point in time. The general procedures outlined below describe how missing data are handled.

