9.4.4. Other Efficacy Endpoints

All the exploratory efficacy analyses will be based on the available data in the ITT population.

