The percent change in wound volume at 2, 2.5, 3, 4, and 7 months from baseline will be summarized for each treatment group and compared between the treatment groups using a linear mixed-effects model for repeated measures². The model will include treatment, visit, and treatment-by-visit interaction as the main fixed effects, and baseline wound volume as a covariate using an unstructured variance-covariance matrix. The point estimates for the least-squares mean of the treatment difference (VM202 – Placebo) at each visit and the corresponding 95% confidence interval and p-value will be summarized. Other variance-covariance structures may be substituted if convergence problems arise using corrected Akaike's information criterion (AICC) to pick from among the following structures: compound symmetry (CS), autoregressive ("AR(1)"), variance components (VC), and Toeplitz (TOEP).

The repeated measures analysis above will be performed for this endpoint for each subgroup identified in Section 7.5 meeting the minimum group size requirement. Differences between treatment groups will be compared adjusting for the subgrouping variable using the repeated measures with the subgrouping variable added as a fixed effect in the modeling.

9.4.4.4. Percent change in wound perimeter, area and depth at 2, 2.5, 3, 4, and 7 months

The analyses on the percent change in wound perimeter, area and depth at 2, 2.5, 3, 4, and 7 months from baseline will be based on statistical methods described in Section 9.4.4.3 with the corresponding baseline wound measurement as the covariate.

_

Vonesh, EF and Chinchilli, VM (1996), Linear and Nonlinear Models for the Analysis of Repeated Measurements, New York: Marcel-Dekker.

9.4.4.5. Proportion of subjects with formation of new ulcers on the target foot by 2, 2.5, 3, 4, and 7 months

The proportion of subjects with new ulcers formed by the 2-, 2.5-, 3-, 4-, and 7- month follow-up visits will be calculated for each treatment group. The 95% confidence intervals of the proportion will be provided based on the binomial distribution and the exact 95% confidence intervals of the proportion difference will also be obtained. Fisher's exact test will be used to compare the proportion between the treatment groups at each time point.

The subgroup analyses described in Section 9.4.2 will be performed for these exploratory endpoints.

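### The SAP gives a closed wound no size, so on a literal reading the four exploratory percent-change analyses lose wounds because they healed

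*SAP*

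**What the plan says.** SAP 5.3.2 states that the four size measures "will be measured using ARANZ Silhouette products at baseline and every scheduled post-baseline visit until wound closure". SAP 3 agrees ("Measurement of the target ulcer will be performed at each follow-up visit until complete wound closure or study exit"), as does the protocol synopsis ("Measurement of target ulcer will be performed at each follow-up visit until complete wound closure is achieved or until study exit"). Protocol 4.2.1 ties ulcer documentation to visits at which the ulcer is present. SAP 8.1 names one source: "All wound measurement data will come from the ARANZ Medical study-specific database".

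SAP 5.4 defines percent change as "The ratio of the arithmetic difference between a value of interest and the baseline value to the baseline value multiplied by 100", so it needs a recorded size. SAP 9.4.4 adds: "All the exploratory efficacy analyses will be based on the available data in the ITT population". Under SAP 9.4.4.3, percent change in volume "will be summarized for each treatment group and compared between the treatment groups using a linear mixed-effects model for repeated measures", with treatment, visit, their interaction, baseline volume and an unstructured covariance. SAP 9.4.4.4 applies the same method to perimeter, area and depth.

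SAP 8.6 opens with "The general procedures outlined below describe how missing data are handled", but its subsections cover only questionnaire items, covariates, and dates and times.

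Other text points both ways. Protocol 3.4.13 to 3.4.17 (Days 60 to 210) list size measurements without condition. The schedules (Protocol Appendix 1, SAP Tables 1 and 2) tick ulcer measurement at every follow-up visit, including the healing-confirmation visit. Yet Protocol 3.2 makes ulcer documentation at Days 60 to 210 conditional, Protocol 3.4.18 lists only a photograph at confirmation, and the schedule footnotes treat the healed ulcer as one that cannot be measured.

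**The concern.** Healing is the best outcome, and on the literal reading it removes a subject from the size analyses at later visits. More subjects disappear from whichever arm heals more. The descriptive tables then mainly compare wounds that stayed open. The mixed model does not reliably repair this: it predicts unobserved values from recorded ones, whereas a closed wound has a known size of zero. A subject who closes before Day 60 has no value at any of the five analysis visits and contributes nothing.

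The text also leaves room for recorded zeros, perhaps only at the closing visit, so two analysts following the documents could produce different tables. The sponsor does write such rules elsewhere: Protocol 4.2.9 gives an unavailable TcPO2 sensor site a default of zero.

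**Working it through.** **Inputs.** Closure by 4 months of 50% to 60% on VM202 and 20% to 30% on placebo (SAP 6); 7 + 5 + 16 + 16 = 44 enrolled (SAP 1); analysis visits at Days 60, 74, 90, 120 and 210 (SAP 4.2). The documents give no mean, SD or trajectory for percent change in this trial, so every trajectory below is an assumption.

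**1. The plan's own figure.** None exists for percent change, but the closure rates can be checked through SAP Table 4. At 50% v 30% with 200 v 100 subjects, the continuity-corrected normal formula gives z = (0.20 - 0.0075 - 1.96 x 0.0607)/0.0579 = 1.27, power 0.898 as stated. Exact Fisher power is 0.918, so the inputs are understood.

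**2. Values missing at Day 120, literal reading.** Assume 29 v 15 subjects (about 2:1).
- Lowest: 29 x 0.50 + 15 x 0.20 = 17.5.
- Highest: 29 x 0.60 + 15 x 0.30 = 21.9.

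This counts every closure by Day 120 as missing; a zero recorded at the closing visit lowers it.

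**3. Subjects with no value at all.** With a constant closure hazard, the share closed before Day 60 is 1 - (1 - p)^(60/120). At 50% v 30% this is 29% v 16%, or 25% overall at 2:1.

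**4. Direction of error.** With a closed wound counted as -100%, an arm mean is p x (-100) + (1 - p) x m, where m is the open-wound mean. Available data give m alone. The planned model was simulated with 200 v 100 subjects, 150 runs per scenario, and sizes after closure missing. Differences are VM202 minus placebo at Day 120, in percentage points:

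| Closure | Open-wound means | All wounds | Open only | Model |
|---|---|---|---|---|
| 50% v 30% | -30 v -30 | -14 | 0 | 0.1 |
| 60% v 20% | -30 v -30 | -28 | 0 | 0.1 |
| 50% v 30% | -20 v -30 | -9 | +10 | +10.3 |
| 30% v 30% | -50 v -30 | -14 | -20 | -20.2 |

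Third row in full: 0.5 x (-100) + 0.5 x (-20) = -60; 0.3 x (-100) + 0.7 x (-30) = -51; difference -9. The first two rows hide the effect, the third reverses its sign and the fourth overstates it.

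If wounds instead shrink linearly to closure (50% v 30%), the all-wound difference is -18.9, the raw available-data difference -13.2 and the model -25.9. At Day 210 the model gives -44.5 against -17.9. Here the model projects fast-healing wounds past -100%.

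**5. No treatment effect.** In six further scenarios (30% closure in both arms, 12,000 per arm), the model difference was off by at most 0.6 points.

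**6. Zero at the closing visit only.** With closure 50% v 30% spread over Days 28 to 120 and open wounds at -40% in both arms, the Day 120 all-wound difference is -11.9; the raw difference is -7.4 and the model gives -17.9. At Day 210 the raw difference is -0.5 against -11.9. One zero does not settle later visits.

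**The case against.** The strongest reply is that missingness is a possible reading and not a stated rule. The visit lists and schedule ticks could lead sites to record a zero, and then the SAP 5.4 formula yields -100% with no further rule. SAP 5.3.2 also reconciles closure with the imaging data where possible. This stands in part: a reader might infer that the SAP instructs analysts to exclude healed wounds, and it does not. But the reconciliation concerns closure status and not size, and the conflicting text means that recorded zeros cannot be relied on.

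The second reply is that little depends on these analyses. They are exploratory (SAP 8.4), closure has its own analyses, and the trial stopped early. With an assumed SD of 30 and all 44 subjects contributing, the standard error of a difference at one visit is 30 x sqrt(1/29 + 1/15) = 9.5 points, so noise rivals many of the errors above. This stands, and it sets the severity.

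The third reply is that the error sizes reflect chosen trajectories. This also stands. A separate set of twelve simulated scenarios at 50% v 30% ran from 5.6 points too large to 12.2 too small at Day 120, and the scenarios tabulated in the working fall outside that range. No numerical bound is supportable.

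**Conclusion.** The gap is real and minor. No rule gives a closed wound a size, and on the literal reading values go missing because of healing. About 18 to 22 of the 44 enrolled could lack a Day 120 value, given the SAP's assumed closure rates and a 29 v 15 split, and fewer if the closing visit carries a zero.

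A reader might infer that the gap consistently hides a benefit of VM202, or that it creates false positives. Neither is supported: with an effect the error ran both ways, and with none the simulations showed no bias in the difference. A reader might also extend the problem to the trial's main result. The primary endpoint, time to closure and closure by 7 months do not use wound size and are untouched. Confidence is high that the rule is absent and that the direction is unpredictable, and low for any particular error size.

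**What to change.** In SAP 5.3.2 and 9.4.4.3 to 9.4.4.4, set area, perimeter, depth and volume to 0 (percent change -100%) at each attended scheduled visit, up to study exit, at which the eCRF documents the target ulcer as closed, or at which it was last documented closed with no documented reopening. In addition:

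- If the ulcer reopens, use the measured value.
- Treat missed visits the same way for healed and unhealed subjects, so that zeros are not filled in for healed subjects alone.
- Do not code an ulcer lost to amputation as closed.
- Amend SAP 8.1 to allow the eCRF-derived zero.
- Apply the rule to both summaries and model, and footnote the number of derived zeros.
- Add a rank-based comparison at each visit as a supportive analysis, because values will cluster at -100%.

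The cost is one derivation rule, one sentence in SAP 8.1, the supportive comparison and a rerun of planned tables, using closure data already on the eCRF page that serves the primary analysis. There are two downsides. The normal model will fit less well. And because weekly visits stop at healing and the primary endpoint no longer requires confirmation, a reopening may be detected late, leaving a zero wrong for a time.

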5. EVALUATION OF ADVERSE EVENTS

5.1. **DEFINITIONS**

An Adverse Event (AE) is the development of an untoward medical occurrence or the deterioration of a pre-existing medical condition following or during exposure to an investigational product, whether or not considered causally related to the product.

An untoward medical condition can be symptoms (e.g., nausea, chest pain), signs (e.g., tachycardia, enlarged liver) or clinically significant abnormal results of an investigation (e.g., laboratory findings, electrocardiogram).

Conditions or diseases that are chronic but stable should not be recorded as an AE. Changes in a chronic condition or disease that are consistent with natural disease progression are NOT considered AEs and also should not be recorded in the AE form of the electronic data capture system (EDC). These medical conditions should be adequately documented on the appropriate form of the study EDC (relevant medical history and/or physical examination). However, medical conditions present at enrollment that worsen in intensity or frequency in a manner inconsistent with the natural course of the disease during the treatment or post-treatment periods should be reported and recorded as AEs.

An **adverse reaction** means any adverse event caused by a drug. Adverse reactions are a subset of all suspected adverse reactions for which there is reason to conclude that the drug caused the event.

Suspected adverse reaction means any adverse event for which there is a reasonable possibility that the drug caused the adverse event. For the purposes of IND safety reporting, 'reasonable possibility' means there is evidence to suggest a causal relationship between the drug and the adverse event. A suspected adverse reaction implies a lesser degree of certainty about causality than adverse reaction, which means any adverse event caused by a drug.

A serious adverse event (SAE) is any untoward medical occurrence which:

- Results in death;
- Is life-threatening;

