9.5.3. Adverse Events

Adverse events will be collected once subjects meet all the study eligibility criteria and are randomized and administered study drug. However, all adverse event summaries will be restricted to Treatment-Emergent Adverse Events (TEAE), which are defined as those AEs that occurred after first dosing and those pre-existing conditions that worsened during the study. If the start time for an AE that occurs on the first date of dosing is unknown, then the event will be assumed to be a TEAE. If the start date of an AE is unknown, the event will be assumed to be a TEAE.

The number of subjects experiencing a particular event, the percentage of subjects experiencing the event, and the total number of events will be presented. The following summaries will be created:

- Overall summary of TEAEs, which includes the subject incidence of TEAEs and total number of unique TEAEs from each of the following AE summaries without regard to MedDRA system organ class or preferred term
- TEAE by SOC and preferred term
- TEAE by SOC and preferred term by injection number. Subjects and events are attributed to a given injection only if the event start date (subject to the missing date and

time imputation rules of Section 8.6.3) occurs on or after the date and time of that injection and not before the next injection.

- TEAE by SOC, preferred term and protocol version
- TEAE by SOC, preferred term and maximum severity. At the across-SOC and preferred term levels of subject summarization, a subject is classified according to the highest severity if the subject reported one or more events; severity within an SOC is not summarized. AEs with missing severity will be considered severe for this summary.
- TEAE by SOC, preferred term and closest relationship to study treatment (Related/Not Related). At each level of subject summarization, a subject is classified according to the closest relationship if the subject reported one or more events. AEs with a missing relationship will be considered 'related' for this summary; events classified as 'possibly', 'probably' or 'definitely' will be considered 'related'.

A listing of treatment-emergent SAEs (if any) will be provided, and if more than one occurs within any given preferred term, a summary of treatment-emergent SAEs by SOC and preferred term will be created.

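### The new-foot-ulcer endpoint is defined by clinical criteria but counted by a keyword scan of adverse event terms that does not apply them

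*SAP*

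**What the plan says.** SAP 5.3.2 states what a new foot ulcer is: "Defined as a newly formed non-healing or poorly healing full-thickness wound, below the ankle on the target foot". It then fixes the source: "these will be identified solely based the AE data provided by the site". The one operation described is a search: "The AE verbatim term will be scanned for the text" ULCER, and for LEFT or RIGHT. The side found is compared with the side of the target limb on the eCRF. There is a default: "if no information on site is present, it will be assumed that the new ulcer is on the target limb".

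The two amputation endpoints in the same section also rely on adverse event (AE) data, but are handled differently: "these will be identified based on a blinded review of the AE data".

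Three statements determine which ulcers can enter the AE data:
- SAP 5.3.1 includes in the definition of an AE "the deterioration of a pre-existing medical condition following or during exposure to an investigational product".
- Protocol 5.1 requires reporting of "medical conditions present at enrollment that worsen in intensity or frequency in a manner inconsistent with the natural course of the disease".
- SAP 9.5.3 describes treatment-emergent events as "those AEs that occurred after first dosing and those pre-existing conditions that worsened during the study".

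SAP 9.4.4.5 reports the proportion of subjects with new ulcers by 2, 2.5, 3, 4 and 7 months, with Fisher's exact test at each time point and subgroup analyses. SAP 8.4 classes the endpoint as exploratory.

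**The concern.** The definition and the counting rule describe different things. The definition needs clinical facts about a lesion, whereas the rule needs only a word and a side. Every subject enters with a foot ulcer, and the rule has no exclusion for it. A count that mixes worsened old ulcers, leg ulcers and true new foot ulcers, and leaves out new lesions described in other words, cannot be read as the new-ulcer rate. Errors need not be equal between arms either, because worsening of the target ulcer is something the treatment might itself affect.

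**Working it through.** No figure in the plan needs reproducing here. The check sets the definition against the rule, follows what can reach the AE data, runs the rule on examples, and then sizes one error.

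**1. Definition against rule.** Protocol 5.2 lists nine items recorded for an AE: description, onset date, duration, frequency, severity, seriousness, treatment, outcome and relationship.

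| Element of the definition | Tested by the scan? | Help from the nine AE items |
|---|---|---|
| Newly formed | No | Onset date |
| Non-healing or poorly healing | No | Outcome, in part |
| Full-thickness | No | No field; free text only |
| Below the ankle | No | No field; free text only |
| Target foot | Side of limb only, with a default | No field; free text only |

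**2. What can reach the AE data.** Newness is partly screened upstream. Events before the first injection go to medical history (Protocol 4.1.1, 5.2), and stable or naturally progressing chronic disease is not an AE (Protocol 5.1, SAP 5.3.1). Worsening beyond the natural course is an AE. That leaves these routes into the count:
- the target ulcer, present in every subject;
- another baseline ulcer on the target foot, allowed since protocol version G (SAP 1) and foreseen in Protocol Appendix 4;
- a same-side leg ulcer. Calf ulceration judged an injection site reaction has its own form (Protocol 4.2.11), so this route concerns other leg ulcers. The SAP does not say whether that form is scanned.

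In the other direction, a lesion not called an ulcer is missed. Protocol 5.2 asks for standard terminology, which lowers this risk. It also asks that secondary events be described in the narrative, and the scan reads only the verbatim term.

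**3. The rule run literally.** It was coded as: ULCER present; side equals target side; no side means target. The terms below are hypothetical and were chosen to probe the rule, so they say nothing about frequency. The target side is right.

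| Term | Meets definition | Counted |
|---|---|---|
| New ulcer right 2nd toe | Yes | Yes |
| New ulcer R hallux | Yes | Yes (by default) |
| Worsening of right foot target ulcer | No | Yes |
| Infected ulcer right foot (index) | No | Yes |
| Right shin venous ulcer | No | Yes |
| Superficial ulceration right heel | No | Yes |
| New ulcer L hallux | No | Yes (by default) |
| Gastric ulcer | No | Yes (by default) |
| Sacral decubitus ulcer | No | Yes (by default) |
| New diabetic foot wound right heel | Yes | No |
| Skin breakdown right great toe, full thickness | Yes | No |

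**4. Size of one error.** SAP 1 gives enrollment by protocol version: 7 + 5 + 16 + 16 = 44, taken here as the ITT number. Subjects enrolled under version G number 16/44 = 36%. This is a ceiling for those with a second baseline ulcer that the version G change admitted; the actual number is not given. The split by arm is not given either, so it is assumed around 2:1. One subject shifts a proportion by 1/n:

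| Assumed split (VM202/placebo) | VM202 | Placebo |
|---|---|---|
| 28/16 | 1/28 = 3.6 points | 1/16 = 6.3 points |
| 29/15 | 1/29 = 3.4 points | 1/15 = 6.7 points |
| 30/14 | 1/30 = 3.3 points | 1/14 = 7.1 points |

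**5. Illustration with assumed error rates.** Observed rate = p × sensitivity + (1 − p) × false-positive rate. Take true rates of 10% and 20%, sensitivity 0.6 and a false-positive rate of 0.15 in both arms. The observed rates are 0.06 + 0.135 = 0.195 and 0.12 + 0.12 = 0.24. The difference falls from 10 to 4.5 points and the risk ratio moves from 0.50 to 0.81. With unequal errors the bias could go either way.

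**The case against.** The strongest reply is that the definition comes first and governs. On that reading the source clause names only where to look, and the default already speaks of a new ulcer and settles only its location. A worsened baseline ulcer would then be excluded by definition. This reading is possible, but the SAP gives no step that applies the definition, so the programmer is left with the scan.

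The default clause says site. If that means anatomical location and not side, location may be used when it is present in the term, which would weaken the leg-ulcer, gastric and sacral examples. The SAP gives no rule for doing so.

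The route for worsened ulcers is narrow, since natural progression is not reported. That stands as a limit on frequency; it does not close the route. The treatment-emergent definition in SAP 9.5.3 governs safety summaries, so it supports the point only indirectly. Injection site events are listed and summarized separately from other AEs, which makes it unlikely that their form is scanned.

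Blinded data screening by the review committee (SAP 8.1) and query resolution before unmasking (SAP 8.3) are real safeguards. They are general, however, and a term that satisfies the scan need not look questionable. The full data listings (SAP 9.1) would show the reported terms but would not correct the table.

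Finally, a prespecified, reproducible rule that ignores treatment arm is defensible for an exploratory endpoint in a trial that stopped early. This supports a low grade. It does not make the rule match its definition.

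**Conclusion.** The concern holds, as a minor point. The stated rule can misclassify new foot ulcers in both directions, and no other provision in the plan checks depth or position below the ankle. How many subjects are affected, and which arm would benefit, cannot be known from the documents. Each error would move a proportion by 3.3 to 3.6 points (VM202) or 6.3 to 7.1 points (placebo), assuming 44 subjects in the ITT population and splits from 28/16 to 30/14. The effect stops at one exploratory endpoint and its subgroup tables. The primary endpoint comes from a different eCRF page.

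**What to change.** Amend SAP 5.3.2 as follows:
- Use the text scan, widened to terms such as wound, only to find candidate events.
- Before unblinding, extend the blinded amputation review to these candidates. Judge each against every element of the definition, using the description, onset date and outcome.
- Exclude the target ulcer and any ulcer recorded at baseline in the medical history.
- Resolve a missing side through the existing query process.
- Where side, depth, position or healing status cannot be determined, flag the event and show the results with and without it.
- State in the clinical study report that new ulcers were captured only through AE reporting.

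The cost is a few lines of SAP text, a short listing review for 44 subjects alongside the amputation review, and a small number of site queries. Widening the search will bring in some wounds that are not ulcers, which the review removes. SAP 4.5 describes a recategorization of wound location already made ahead of database lock, so time for new queries is not assured. Any side left unresolved would go into the with-and-without display. No new data collection is needed.
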